### 5.6.2. Analyses of Secondary Efficacy Variables

The key secondary efficacy endpoints (defined in [Section 4.6.2](#)) and other secondary efficacy endpoints (described in [Section 4.6.3](#)) for the double-blind period, descriptive summaries and analyses will be performed in the ITT population or mITT population, corresponding to the specified estimand for the endpoint.

For descriptive summaries, percent change, and when appropriate, absolute change from baseline in LDL C, total-C, HDL-C, TG, and non-HDL-C will be provided at each time point for each treatment group. All measurements, scheduled or unscheduled, will be assigned to analysis windows defined in [Appendix 10.2](#) in order to provide an assessment for these time points. Laboratory assessments other than the ones provided by the central laboratory will be excluded. For TGs, measurements on not-fasting patients will be excluded. The time profile of each parameter will be plotted by treatment group with the corresponding standard errors. Similar tables (with either percent change from baseline or absolute change from baseline for the ratio) and plots will be provided for other efficacy parameters: Apo B, Apo A-1, ratio Apo B/Apo A-1, Lp(a).

Multiple types of measurements are planned to be analyzed during differing time points in the trial, specifically continuous measurements expected to have a normal distribution (example: percent change in LDL-C), continuous measurements expected to have a non-normal distribution (example: TG), and binary measurements (example: proportion of patients with at least 30% reduction in LDL-C).

#### 5.6.2.1. Continuous Endpoints Anticipated to have a Normal Distribution

Continuous secondary variables defined in [Section 4.6.2](#) and [4.6.3](#) anticipated to have a normal distribution (i.e. lipids other than TG and Lp(a)) will be analyzed using the same MMRM model as described for the primary endpoint. Specifically, the model will contain the fixed categorical effects of treatment group, randomization strata (as per IVRS/IWRS), planned time points up to week 12, strata-by-time point and treatment-by-time point interaction, as well as, the continuous fixed covariates of corresponding baseline value and baseline value-by-time point interaction.

### 5.6.2.2. Continuous Endpoints Anticipated to have a Non-normal Distribution

Continuous secondary efficacy variables defined in [Section 4.6.2](#) and [4.6.3](#) anticipated to have a non-normal distribution (i.e. TG and Lp(a)) will be analyzed using the same multiple imputation approach for handling of missing values as described for primary efficacy endpoint (and using the same time points in the imputation model as described above for [Section 5.6.1.2](#)), with data log-transformed before imputation process and then back transformed to create the imputed data sets using the TRANSFORM statement of SAS MI procedure.

The percent change from baseline at time point of interest will be derived from observed and imputed lipid values at this time point. Multiple imputation will be followed by robust regression model [\(5\)](#) to compare treatment group differences, with the endpoint of interest as the response variable using M-estimation (using SAS ROBUSTREG procedure) with treatment group, randomization strata (as per IVRS/IWRS) and corresponding baseline value(s). Combined means estimates for both treatment groups, as well as the differences of these estimates, with their corresponding SEs, 95% CIs and p-value will be provided through the SAS MIANALYZE procedure.

### 5.6.2.3. Binary Endpoint Variables

Binary secondary efficacy endpoints defined in [Section 4.6.2](#) and [4.6.3](#) will be analyzed using the multiple imputation approach for handling of missing values as described for the primary efficacy endpoint (and using the same time points in the imputation model as described above for [Section 5.6.1.2](#)).

The binary endpoint at time point of interest will be derived from observed and imputed lipid values at this time point. Multiple imputation will be followed by stratified logistic regression, (with strata defined as randomized in the IVRS/IWRS) using the strata option of the SAS logistic procedure. The logistic regression procedure will be used to compare treatment group differences, with the model containing treatment group and corresponding baseline value(s) as covariate, stratified by randomization strata defined as per IVRS/IWRS. Combined estimates of odds ratio versus placebo, 95% CI, and p-value will be obtained through the SAS MIANALYZE procedure.

In the data dependent case such logistic regression is not applicable (e.g. the response rate is zero in one treatment arm and thus the maximum likelihood estimate may not exist), the last observation carried forward (LOCF) approach would be used for handling of missing values. Treatment effects would be compared using the stratified exact conditional logistic regression method, specifically using the strata option of the SAS logistic procedure (with strata defined as randomized in the IVRS/IWRS). In case the model would not converge with stratification variables, an unstratified exact logistic regression will be performed. The LOCF imputation method will consist of using the last value obtained up to the week 12 analysis window to impute the missing week 12 value.

In case of computing issues with exact logistic regression, the baseline level(s) will be entered in the model as a categorical variable(s) using quartiles. Exact odds ratio versus placebo, 95% CI, and p-value will be provided.

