#### III. Binary endpoints

Binary secondary efficacy endpoints defined in Section 4.2.2 will be analyzed in the analysis populations using stratified logistic regression (using the strata option of the SAS logistic procedure) with treatment group as main effect and corresponding baseline value(s) as covariate, stratified by randomization factor (as per IVRS). Missing values will be addressed using a multiple imputation approach which will be described in the SAP. The variables in the multiple imputation model will at least include the same variables as used in the logistic regression model. Treatment effects will be compared and the combined odds ratio estimate between the treatment groups, with their corresponding 95% CIs and p-value will be provided. In the data dependent case that the logistic regression method is not applicable (eg, the response rate is zero in 1 treatment arm and thus the maximum likelihood estimate may not exist), the last observation carried forward approach would be used for handling of missing values and an exact conditional logistic regression would be performed to compare treatment effects. The last observation carried forward imputation method will consist of using the last value obtained up to the week 12 time window to impute the missing week 12 value.

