### ***Pattern mixture model***

The MMRM model relies on the “missing-at-random” (MAR) assumption. Because the possibility for a not-missing-at-random (NMAR) missingness mechanism can never be excluded, sensitivity analysis to explore the impact of non-ignorable missingness on the primary efficacy analysis will be conducted using the pattern mixture model approach as described below (see [Appendix 10.7](#) for more details).

In the pattern-mixture model approach, different imputation strategies will be applied to LDL-C values missing during the double-blind on-treatment period (i.e. within the time period from the first double-blind study treatment injection up to the day of last double-blind injection +21 days or day of the first open-label injection whichever comes first) versus LDL C values missing after treatment discontinuation (i.e. after the day of last double-blind injection +21 days) based on the following assumptions:

- Patients within 21 days of their last double-blind IMP injection would continue to show benefit from treatment similar to that observed at the scheduled time point. Therefore, LDL-C values missing during the on-treatment period (e.g., samples obtained out-side the specified window, no blood sample available although visit was performed, etc.) should be considered “Missing At Random” and imputed based on other on-treatment measurements.
- Patients who stopped taking their study treatment no longer benefited from it after discontinuation, and thus tended to have LDL-C values returning to baseline. Therefore, LDL-C values missing after treatment discontinuation should be imputed based on patient’s own baseline value.

Missing data from the randomized population will be imputed 100 times to generate 100 complete data sets, using the approach described above. The 100 completed datasets of observed and imputed LDL-C data will be used for primary efficacy analyses.

The 100 complete datasets of observed and imputed LDL-C data at week 12 will be analyzed using an ANCOVA model with treatment group and randomization strata as fixed effect, and the baseline LDL C value as continuous covariate. The MIANALYZE SAS procedure will be used to generate valid statistical inferences by combining results from the 100 analyses using Rubin’s formulae (4).

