## 10. APPENDIX

### 10.1. Summary of Statistical Analyses

#### Primary Efficacy Analysis:

Endpoint	Analysis Populations	Statistical Method	Supportive Analysis	Subgroup Analysis	Other Analyses
Percent change from baseline in LDL-C at week 12	ITT	MMRM	Yes, including handling of missing data	Yes	1) On-treatment estimand 2) Actual stratification factor 3) Multiple Imputations + ANCOVA 4) Pattern mixture model

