## 10.6. Detailed Description of the Multiple Imputation Procedure

The following is a detailed description of the multiple imputation procedure which will be used for sensitivity analysis of primary efficacy endpoint as well as the analysis of the secondary efficacy endpoints.

In general, the missing pattern is anticipated to be not monotone, a two-step approach will be used:

- Step 1: the MCMC method will be used in conjunction with the IMPUTE=MONOTONE option to create an imputed data set with a monotone missing pattern.
- Step 2: Using the monotone data set from step 1, missing data will be imputed using the regression method.

The imputation model for step 1 will include the treatment group and the values of the analyzed parameter at baseline and planned time-points up to week 12.

The imputation model for step 2 will include the same variables as in step 1 with the following additional variables:

- the randomization strata (apheresis treatment status strata);
- age, BMI, and gender (age and BMI included as continuous variables).

Non-continuous variables included in the imputer's model (i.e., treatment group, randomization strata and gender) are not expected to be missing.

In addition, for continuous efficacy variables anticipated to have a non-normal distribution (i.e. TG and Lp(a)), data will be log-transformed before imputation process and then back-transformed to create the imputed data sets using the TRANSFORM statement of SAS MI procedure.

For variables other than those continuous efficacy variables anticipated to have a non-normal distribution (i.e. TG and Lp(a)), for each simulation leading to negative imputed value, another value will be redrawn using MINIMUM option of MI SAS procedure.

The number of imputations (100) will be informally verified by replicating sets of 100 imputations and checking whether the combined results are stable. If not stable, the number of imputations will be increased and informally checked as above, and thus continued until stable estimates are obtained.

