## 10.7. Detailed Description of Pattern Mixture Model

As a sensitivity analysis of the primary efficacy endpoint (i.e. percent change from baseline to Week 12 in LDL-C), a pattern-mixture model approach will be used, with a different imputation strategy applied for missing LDL-C values during the on-treatment period (i.e. within the time period from the first double-blind IMP injection up to the day of the last double-blind injection +21 days or to the day before the first open-label injection, whichever comes first) and missing LDL-C values after treatment discontinuation (i.e. after the day of last injection +21 days) based on the following assumptions:

- Patients within 21 days of their last IMP injection would continue to show benefit from treatment similar to that observed at the scheduled time point. Therefore, LDL-C values missing during the on-treatment period will be considered “Missing At Random” and imputed using a model estimated using all samples collected on treatment.
- Patients who stopped taking their study treatment no longer benefited from it in the future, and thus tended to have LDL-C values returning to baseline. Thus LDL-C values missing after treatment discontinuation will be imputed based on patient’s own baseline value.

[figure not shown]
The assumptions for this approach are based on the following considerations:

- Missing values during the on-treatment period are mostly consecutive to:
  - Visits performed outside of the pre-specified time-window
  - No blood sample available although visit was done
  - LDL-C not measurable due to technical reasons

[figure not shown]
In addition, these missing data are often intermittent, i.e. followed by LDL-C values collected at subsequent visits. It is therefore considered reasonable to assume that these missing data were “At Random”.

Phase 2 studies DFI11565 and R727-CL-1003 included a prospective assessment of calculated LDL-C during the follow-up period after a 12-week treatment period. These studies showed that after treatment discontinuation, the average calculated LDL-C returned to baseline level within 4 weeks after ceasing Praluent treatment (see [Figure 2](#) and [Figure 3](#)).

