### **Imputation of missing data after treatment discontinuation**

Missing LDL-C values during the post-treatment period will be imputed assuming LDL-C values would on average return to baseline values.

For each patient, missing post-treatment LDL-C values will be imputed 100 times, using a random draw from a normal distribution, with mean equal to patient's own baseline value and variance equal to the conditional variance at the specific time-point, given the baseline value.

Let  $Y_0$  and  $Y_1$  denote the LDL-C at baseline and at the specific time-point respectively. Since  $Y_0$  and  $Y_1$  are assumed to have a bivariate normal distribution, the conditional variance of  $Y_1$  given  $Y_0$  is:

$$Var(Y_1|Y_0 = y_0) = \sigma_1^2(1 - \rho^2)$$

Where  $\sigma_1^2$  denotes the variance of Y1 and  $\rho$  the coefficient of correlation between  $Y_0$  and  $Y_1$ .

The conditional variance will be estimated from observed data within the same treatment arm at the specific time-point.

During the random generation process, a minimum value of 0 will also be applied in order to avoid negative imputed LDL-C values.

Signature Page for VV-RIM-00084723 v1.0

ESig Approval	[REDACTED]
	12-Aug-2019 16:13:53 GMT+0000
ESig Approval	[REDACTED]
	12-Aug-2019 17:06:50 GMT+0000
ESig Approval	[REDACTED]
	12-Aug-2019 22:28:04 GMT+0000
ESig Approval	[REDACTED]
	13-Aug-2019 18:57:05 GMT+0000
ESig Approval	[REDACTED]
	13-Aug-2019 18:59:40 GMT+0000
ESig Approval	[REDACTED]
	14-Aug-2019 20:28:32 GMT+0000

Signature Page for VV-RIM-00084723 v1.0 Approved

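### No planned responder analysis imputes loss of effect for Week 12 LDL-C values that are missing after study drug is stopped

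*SAP*

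**What the plan says.** The three responder endpoints are fourth, fifth and seventh of the ten key secondary endpoints (SAP 4.6.2). They carry the ITT estimand and sit in a fixed sequence in which each test opens the next (SAP 5.6.3).

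- **Main analysis.** Under SAP 5.6.2.3 they "will be analyzed using the multiple imputation approach for handling of missing values as described for the primary efficacy endpoint". In Appendix 10.6 the first-step imputation model "will include the treatment group and the values of the analyzed parameter at baseline and planned time-points up to week 12"; the second step adds apheresis stratum, age, BMI and gender. Neither step marks whether the patient had stopped drug.
- **Fallback.** If logistic regression is not applicable, for example because one arm has no responders, "the last observation carried forward (LOCF) approach would be used for handling of missing values", followed by an exact conditional test. Protocol 10.4.3.2 III describes this as "using the last value obtained up to the week 12 time window to impute the missing week 12 value". It draws no on-drug/off-drug distinction.
- **Primary endpoint only.** SAP 5.6.1.2 says "sensitivity analysis to explore the impact of non-ignorable missingness on the primary efficacy analysis will be conducted using the pattern mixture model approach". Appendix 10.7 opens "As a sensitivity analysis of the primary efficacy endpoint" and states: "Missing LDL-C values during the post-treatment period will be imputed assuming LDL-C values would on average return to baseline values". The primary-endpoint row of Appendix 10.1 lists "1) On-treatment estimand 2) Actual stratification factor 3) Multiple Imputations + ANCOVA 4) Pattern mixture model".
- **Sensitivity analysis of the key secondaries.** SAP 5.6.2.4 repeats the same methods on efficacy-treatment-period data in the mITT population.

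**The concern.** The SAP supplies the contrary premise itself. Section 5.6.1.2 assumes that patients who stop drug lose its benefit, and Appendix 10.7 cites two Phase 2 studies of alirocumab in which mean LDL-C was back at baseline within 4 weeks of stopping. The responder endpoints are cut-points of the same Week 12 LDL-C in the same patients. A value missing after discontinuation is tested at baseline for the primary endpoint and never for the responders. The on-treatment mITT analysis asks a different question and cannot test that assumption.

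If the drug works, any systematic error favours alirocumab, because a placebo patient has no drug effect to carry forward. At stake is a slight overstatement of responder rates, and so of the chance of passing three steps of the hierarchy.

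**Working it through.** **1. Inputs and the plan's own figure.** SAP 2.2 gives about 74 patients at 2:1 (taken as 49 and 25), a blinded adjusted SD of 35, a 20-point difference, 5% non-evaluable and two-sided 0.05. Removing 5% leaves about 70. A two-sample t-test then has power 60.0% (47 vs 23) to 60.9% (46 vs 24), which reproduces the stated 61% for the primary endpoint. The documents give no expected rate or power for the responder endpoints.

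**2. Who can be affected.** The Week 12 target is Day 85. A last injection at Day 57 gives 57 + 21 = 78, before Day 85, so a missing value counts as after discontinuation. A last injection at Day 71 gives 71 + 21 = 92, so Day 85 is still on treatment. If the whole 5% allowance is charged to stoppers, 0.05 × 49 = 2.45, so three is taken as the ceiling.

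**3. Shift in the alirocumab responder rate.** Assumptions not in the documents: normal percent changes, placebo mean 0, alirocumab mean μ = −20 (the planning difference) or −40 (illustrative). For threshold t and SD σ, a missing value counts as a response with probability Φ((−t−μ)/σ) under missing-at-random and Φ(−t/σ) under return to baseline. Shift = 3 × (difference)/49. At σ = 35:

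| Threshold | Return to baseline | MAR, μ=−20 | Shift | MAR, μ=−40 | Shift |
|---|---|---|---|---|---|
| ≥15% | 33.4% | 55.7% | 1.4 points | 76.2% | 2.6 points |
| ≥30% | 19.6% | 38.8% | 1.2 points | 61.2% | 2.6 points |
| ≥50% | 7.7% | 19.6% | 0.7 points | 38.8% | 1.9 points |

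At the original planning SD of 20 the same formula gives 2.3/1.5/0.4 points (μ=−20) and 4.1/3.8/1.9 points (μ=−40).

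**4. Chance of p<0.05, three stoppers.** Simulation: 20,000 trials per case, SD 35, assumed Week 8 to Week 12 correlation 0.7, 100 imputations, log odds ratios pooled by Rubin's rules. Trials with no placebo responder used Fisher's test, with LOCF compared with non-response.

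| Threshold | μ=−20: MAR → return to baseline | μ=−40: MAR → return to baseline |
|---|---|---|
| ≥15% | 43.3% → 40.0% | 95.7% → 92.9% |
| ≥30% | 36.2% → 32.8% | 94.7% → 91.3% |
| ≥50% | 16.1% → 13.5% | 84.7% → 79.7% |

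The falls are 2.5 to 5.0 points. One-stopper results are not used. At ≥15% and μ=−20, one stopper gave a fall of 2.6 points (43.4% to 40.8%) against 3.3 for three. That lack of proportion reflects the discreteness of an unadjusted 2×2 comparison.

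**5. The fallback.** The chance of no placebo responder is (1 − Φ(−t/σ))^25. At ≥50% this is 14% at SD 35 and 86% at SD 20; at ≥30% and SD 35 it is 0.4%. Against 0/25, Fisher's test gives p = 0.0875 for 7/49 and 0.0454 for 8/49, so one carried-forward responder can decide the result. Take m stoppers, k ~ Bin(49−m, p) responders among the rest and L ~ Bin(m, p) carried forward, with p = Φ((−50−μ)/σ). The chance that LOCF alone makes ≥50% significant is P(0 of 25) times the probability that k alone is not significant but k+L is. With m = 3, its maximum over μ from −10 to −50 is 1.0% at SD 35 (μ=−16) and 6.5% at SD 20 (μ=−31).

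**Limits.** Fisher's test and an unadjusted odds ratio stand in for the planned stratified, baseline-adjusted models.

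**The case against.** A reader might infer that no responder analysis allows for loss of effect after stopping. The documents do not support that. The ITT estimand uses LDL-C regardless of adherence (SAP 4.6.1), and Protocol 4.2.2.1 applies the same rules to the key secondaries. Protocol 7.4.2 keeps stoppers in the study and asks for every effort to obtain Week 12. Observed off-drug values therefore enter the main analysis, the imputation and LOCF. Only missing values are at issue.

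The affected group is also easy to overstate. Appendix 10.7 expects on-treatment gaps to come mostly from out-of-window visits, absent samples or technical failures, which are a different matter. The Week 12 window runs from Day 71 to at most Day 98 (Appendix 10.2, Table 1a), so a Week 10 or unscheduled sample can fill it. Three is a ceiling, and the group may be empty. This stands.

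Nothing promises the pattern-mixture model for secondary endpoints; Protocol 10.4.3.1 plans it for the primary. The primary version will already hint at whether these values matter, and Apo B, non-HDL-C and total cholesterol have no such check either. That is fair, and it is why the point is minor. But a mean difference does not show what happens at a cut-point, and for the responders the imputed LDL-C data sets will already exist.

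Finally, changing the fallback makes the confirmatory assumption depend on whether an arm has no responders. It already does: the plan switches from a missing-at-random imputation to LOCF at that point. The remaining difference should be stated openly.

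**Conclusion.** The point holds as a minor gap. No planned responder analysis imputes loss of effect for Week 12 values missing more than 21 days after the last double-blind injection. The SAP does not call the Appendix 10.6 imputation missing-at-random; that is inferred from its variables.

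With three stoppers at SD 35, return to baseline lowers the alirocumab responder rate by 0.7 to 2.6 points and the chance of p<0.05 by about 3 to 5 points. This rests on normality, a placebo mean of 0, all affected patients being on alirocumab, and the 5% allowance being used in full. More missing data would enlarge it. The fallback figures depend heavily on the SD.

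Two stronger readings should be resisted. It is not a type I error problem: with no drug effect there is no benefit to carry forward. Nor does it touch the primary result, which has its own return-to-baseline analysis.

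**What to change.** 1. In SAP 5.6.2.4, pre-specify a sensitivity analysis that derives the three responder endpoints from the Appendix 10.7 imputed LDL-C data sets and analyses them as in 5.6.2.3.
2. In the 5.6.2.3 fallback, restrict LOCF to values missing within 21 days of the last double-blind injection. Count values missing later as non-response, by setting them to the patient's own baseline. The exact test needs one completed data set, and a zero change is non-response at all three thresholds.
3. State that item 2 differs from the missing-at-random main analysis and is somewhat stricter than the Appendix 10.7 draws. With SD 35 as a stand-in, Φ(−50/35) = 7.7% of such draws would still be a ≥50% response. The share is higher at the lower thresholds (step 3 of the working), where the fallback is less likely to be needed.
4. List item 2 in SAP 1.2.3 as a change from Protocol 10.4.3.2 III, and make all changes before the first-step database lock.

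The cost is a few sentences, one entry in 1.2.3, minor programming that reuses the Appendix 10.7 code, and a slightly lower alirocumab responder rate where the new rule applies. If no patient is affected, results should barely change and robustness is documented.
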